6.2 Sample Size

The sample size will comprise of 120 participants per study arm (120 cases + 120 controls).

Based on preliminary data: at least 116 subjects will allow us to detect an IL-6 difference of 25% at a two-sided alpha of 0.1% and power of 90% (multiple markers were tested, giving similar or smaller group; TNF- α – 58 subjects). 87 subjects/group for a 25% difference in CD8+CD25+ T cell ($\alpha=0.1\%$, power - 90%). These analyses take into account multiple comparisons which are foreseen for immune signature determination.

We believe that these projected effect sizes would potentially be clinically meaningful and credible.

7. Study Closure or Definition of End of Trial

The study will end when:

- Final participants attend last study visit

OR

- i. The planned sample size has been achieved;
- ii. There is insufficient funding to support further recruitment, and no reasonable prospect of additional support being obtained;
- iii. Recruitment is so poor that completion of the trial cannot reasonably be anticipated.

8. Data Handling

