1.2 Rationale

Understanding of the inflammatory and immune nature of hypertension is currently based on studies in rodent models of hypertension, but is supported by human epidemiological and GWAS studies. It is now essential to identify key checkpoints and mechanisms of inflammatory mechanism(s) of human hypertension in comprehensive and sufficiently powered studies, which will then be able to guide subsequent in-depth hypothesis-driven mechanistic studies. This approach may provide the basis for future randomized clinical trials (RCTs).

By interrogating the key hypothesis that inflammatory dysregulation fundamentally controls development of hypertension and vascular remodelling, **InflammaTENSION** provides a new paradigm for the management of the disease, with the potential to lead to the identification of novel therapeutic targets to control blood pressure

and limit target organ damage.

We hypothesize that primary hypertension is associated with distinct pattern of changes within immune/inflammatory systems consisting of cytokines/chemokines and individual immune cell populations.

The data generated from the InflammaTENSION study will be invaluable for identification of novel biomarkers and therapeutic targets in hypertension.

Biomarker analysis will be carried out using standard laboratory techniques for cytokines and chemokines as follows;

Luminex (Invitrogen Cytokine/Chemokine/Growth Factor 45-Plex Human ProcartaPlex™ Panel 1

Target List: BDNF; Eotaxin/CCL11; EGF; FGF-2; GM-

CSF; GRO alpha/CXCL1; HGF; NGF beta; LIF; IFN alpha; IFN gamma; IL-1 beta; IL-1 alpha; IL-1RA; IL-2; IL-4; IL-5; IL-6; IL-7; IL-8/CXCL8; IL-9; IL-10; IL-12 p70; IL-13; IL-15; IL-17A; IL-18; IL-21; IL-22; IL-23; IL-27; IL-31; IP-10/CXCL10; MCP-1/CCL2; MIP-1 alpha/CCL3; MIP-1 beta/CCL4; RANTES/CCL5; SDF-1 alpha/CXCL12; TNF alpha; TNF beta/LTA; PDGF-BB; PLGF; SCF; VEGF-A; VEGF-D

O-Link:Proseek® Multiplex Inflammation I96×96 is a high-throughput, multiplex immunoassay enabling analysis of 92 inflammation-related protein biomarkers across 96 samples simultaneously. This high level of multiplexing is achieved without any compromise on data quality, thanks to our proprietary Proximity Extension Assay (PEA) technology

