4.5 Study Outcome Measures

4.5.1 Primary Outcome Measure

Cytokine and cellular immune signature of primary hypertension.

Association between hypertensive status assessed by ABPM and immune signature analysed as a whole as well as individual pro- and anti- inflammatory cytokine levels and discreet immune cell populations.

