6.1 Statistical Analysis Plan

The InflammaTENSION study will have a comprehensive Statistical Analysis Plan, which will govern all statistical aspects of the study, and will be authored by the Study Statistician ([name]). To gain additional insight, variable selection analysis will be used to identify the best predictors of hypertension and its vascular outcomes (endothelial function/vascular compliance). To do this we will draw the expertise of local bioinformaticians ([name]) and of [name], a theoretical immunologist at University of Glasgow with experience in the modeling of cytokine networks and in machine learning approaches to TCR repertoire analysis. We anticipate using exploratory unsupervised approaches such as Principle Component Analysis and clustering may be used on the cytokine profiles to identify signature patterns of cytokine expression that may allow a reduction of dimensionality. One can also associate each patient's cytokine profile with a score - either one dimensional measure of disease severity or perhaps multi-factorial measures, combining severity with demographic data, for example, and use supervised learning approaches such as support vector machines or neural networks to generate classifiers or predictors of outcomes.

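### Does the 0.1% alpha in section 6.2 fail to cover the number of markers the study will measure?

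*Combined protocol and SAP*

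**What the plan says.** Section 6.2 plans 120 cases and 120 controls. For the most demanding marker quoted, it states that "at least 116 subjects will allow us to detect an IL-6 difference of 25% at a two-sided alpha of 0.1% and power of 90"%. It gives 58 subjects for TNF-alpha, and "87 subjects/group for a 25% difference in CD8+CD25+ T cell" at the same alpha and power. It closes the calculation with "These analyses take into account multiple comparisons which are foreseen for immune signature determination".

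Section 1.2 introduces the assays with "Biomarker analysis will be carried out using standard laboratory techniques for cytokines and chemokines as follows". It lists a "45-Plex Human ProcartaPlex" panel, whose named targets count to 45, and a "multiplex immunoassay enabling analysis of 92 inflammation-related protein biomarkers across 96 samples simultaneously".

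Section 4.5.1 makes the primary outcome the association of hypertensive status with the immune signature as a whole, "as well as individual pro- and anti- inflammatory cytokine levels and discreet immune cell populations".

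Section 6.1 says the study "will have a comprehensive Statistical Analysis Plan, which will govern all statistical aspects of the study". It then describes variable selection, principal components, clustering and supervised classifiers, and gives no multiplicity rule for single markers.

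**The concern.** Section 6.2 asserts that multiplicity is already dealt with, yet the only support is the figure of 0.1%. A reader cannot tell whether it stands for family-wise error or false discovery rate, at what overall level, or over how many tests. On the most familiar reading, 0.05 divided by 50, it fits the 45-plex alone and falls short of the two panels together, before any cell populations are counted.

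Two things would be at stake. The first is the false-positive rate attached to individual markers reported as part of the signature. The second is the 90% power for IL-6, whose requirement of 116 lies just under the planned 120. The same paragraph also writes per group for the T-cell marker but not for IL-6 or TNF-alpha.

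**Working it through.** **Inputs.** From section 6.2: alpha 0.001 two-sided, power 90%, a 25% difference for IL-6 and the T-cell marker, sizes 116 (IL-6), 58 (TNF-alpha) and 87 per group (CD8+CD25+), and 120 per group planned. From section 1.2: 45 and 92 proteins. Assumptions: 5% family-wise error as benchmark, 116 and 58 read as per group, and 25% also applied to TNF-alpha.

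**The plan's own figure.** The protocol gives no standard deviation or coefficient of variation (CV), so 116 cannot be reproduced independently. It can be solved backwards by the normal approximation, n = 2(z_alpha + z_beta)²/d²:

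- z_alpha + z_beta = 3.291 + 1.282 = 4.572
- IL-6: d = 4.572 × √(2/116) = 0.600, implied CV = 0.25/0.600 = 0.42
- CD8+CD25+: d = 4.572 × √(2/87) = 0.693, implied CV 0.36
- TNF-alpha: d = 4.572 × √(2/58) = 0.849, implied CV 0.29

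**Tests covered by 0.1%.** 0.05/0.001 = 50 at 5% family-wise error, and 0.10/0.001 = 100 at 10%.

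**Proteins measured.** At least 92, if every 45-plex target is also on the 92-plex. At most 45 + 92 = 137, if none is. The 92-plex content is not listed, so the range cannot be narrowed. These are proteins measured, not a stated number of primary tests.

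**Error at 0.1% per marker, if no marker truly differs.** Expected false positives = m × 0.001. Family-wise error for independent tests = 1 − 0.999^m.

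| m | expected false positives | family-wise error |
|---|---|---|
| 45 | 0.045 | 4.4% |
| 92 | 0.092 | 8.8% |
| 137 | 0.137 | 12.8% |

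Positive correlation between markers lowers the last column. At an assumed common correlation of 0.3 it is 7.0% for 92 and 9.5% for 137.

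**Power at 120 per group if Bonferroni at 5% were applied.** Power = Φ(d√60 − z_alpha). For IL-6, d√60 = 4.650.

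| alpha | z_alpha | IL-6 | CD8+CD25+ | TNF-alpha |
|---|---|---|---|---|
| 0.001 | 3.291 | 91.3% | 98.1% | 99.9% |
| 0.05/92 = 0.000543 | 3.458 | 88.3% | 97.2% | 99.9% |
| 0.05/137 = 0.000365 | 3.564 | 86.1% | 96.4% | 99.9% |

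The IL-6 difference detectable with 90% power, (z_alpha + 1.282)/√60 × CV, moves from 24.6% to 25.5% and 26.1% across the three rows. Keeping 90% power at 25% would need 125 or 131 per group for IL-6, and fewer than 120 for the other two markers.

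**False discovery rate instead.** The Benjamini-Hochberg cut-off for k declared markers is k × 0.05/m. With m = 92 and k = 2 it is 0.00109. With m = 137 and k = 3 it is also 0.00109. From that point the per-marker cut-off is no stricter than the planning alpha. With a single declared marker it equals Bonferroni, and the IL-6 figures in the lower two rows apply.

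**The case for a change.** The best case for a change is that section 6.2 does not defer the matter. It says in the present tense that the comparisons are accounted for, and that sentence supports the sample size, so it ought to be checkable where it stands. Individual cytokines and cell populations are part of the primary outcome, section 1.2 calls for sufficiently powered studies, and section 1.2 also foresees using a distinct signature to stratify patients. Naming the criterion and the family would cost a few sentences.

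Much of this stands: the protocol states neither, and the sentence cannot be verified from the text. It does not follow that the sentence is wrong. The shortfall appears only when the reader supplies 5% family-wise error and treats every measured protein as a primary test. Section 4.5.1 speaks of cytokines, while the 45-plex also contains growth factors such as BDNF and HGF. A primary family below 50 is therefore compatible with the text, although an unstated number of cell populations pushes the count the other way. The whole-signature part of the outcome and the multivariate methods in section 6.1 are not governed by a per-marker alpha at all.

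**Conclusion.** No change to the plan is needed. Used as written, 0.1% per marker is a strict threshold: about 0.1 expected false positives over either panel count (0.09 to 0.14) if nothing differs. That is acceptable for an observational study that section 2 itself calls a pilot.

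What is missing is a written decision rule, and section 6.1 assigns all statistical matters to a separate Statistical Analysis Plan. Choosing between false discovery rate and Bonferroni there is a trade-off, and neither choice undermines the sample size. The worst case examined costs IL-6 about 2 to 4 points below 90% power and moves its detectable difference to at most 26.1%. These figures rest on 116 per group, the CV solved back from it, and 92 to 137 tests. Cell populations would add to that count, by a number the documents do not give.

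The missing words per group after 116 and 58 look clerical. The figures follow directly on 120 per arm, and the parenthesis that contains 58 speaks of group size. If 116 were a total, IL-6 power would be about 99.9% and there would be no shortfall to discuss.

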8.1 Case Report Forms / Electronic Data Record

An electronic case report form (e-CRF) will be used to collect study data. The e-CRF will be developed by the study data centre at the CASTOR EDC (<https://castoredc.com>) and access to the e-CRF will be restricted, with only authorised site-specific personnel able to make entries or amendments to their Participants' data. It is the investigator's responsibility to ensure completion and to review and approve all data captured in the e-CRF.

All data handling procedures will be detailed in a Study Specific Data Management Plan. Data will be validated at the point of entry into the e-CRF and at regular intervals during the study. Data discrepancies will be flagged to the study site and any data changes will be recorded in order to maintain a complete audit trail (reason for change, date change made, who made change).

8.2 Record Retention

As discussed above in patient recruitment procedures, subjects will be initially identified by a member of the patient's existing clinical care team who has access to patient records in relation to clinical service. They will inform the patient about the possibility of participating in a study.

Patient data will be pseudo-anonymised with a study number given to the patient. This study number will be used for blood tubes. To enable evaluations and/or audits from regulatory authorities, the investigator agrees to keep records, including the identity of all participating subjects (sufficient information to link records), all original signed informed consent forms, in accordance with ICH GCP, local regulations, or as specified in the Clinical Study Agreement, whichever is longer. Data will be retained at the Data Centre for a minimum of 10 years.

Only the Chief Investigator, who is a member of the direct care team, will have access to the participants' personal data during the study. These procedures will comply with the 1998 Data Protection Act. Biological samples collected from participants as part of this study will be transported, stored, accessed and processed in accordance with national legislation relating to the use and storage of human tissue for research purposes and such activities will meet the requirements as set out in the 2004 Human Tissue Act and the 2006 Human Tissue (Scotland) Act.

Personal data will be stored on NHS password protected computers, which are secured as per local NHS protocols. No personal patient details will be on the University computers.

Manual files with personal information will be kept in a secure location in the Clinical Research Facility, containing copies of the consent forms and a sample collection record.

Only members of the study team will have access to any of the data generated.

To enable evaluations and/or audits from regulatory authorities, the data will be retained at the Data Centre for 15 years. The data records will include including the identity of all participating subjects, (to ensure the subjects information can be linked to records), all original signed informed consent forms, source documents, and detailed records of treatment disposition in accordance with ICH GCP, local regulations.

9. Protocol Amendments

Any change in the study protocol will require an amendment. Any proposed protocol amendments will be initiated by the principle investigators and any required amendment forms will be submitted to the regulatory authority, ethics committee and sponsor. The principle investigators will liaise with study sponsor to determine whether an amendment is non-substantial or substantial. All amended versions of the protocol will be signed by the principle investigator and Sponsor representative. Before the amended protocol can be implemented favourable opinion/approval must be sought from the original reviewing Research Ethics Committee and Research and Development (R&D) office(s).

10. Ethical Considerations

10.1 Ethical conduct of the study

The study will be carried out in accordance with the World Medical Association Declaration of Helsinki (1964) and its revisions (Tokyo [1975], Venice [1983], Hong Kong [1989], South Africa [1996] and Edinburgh [2000]).

Favourable ethical opinion will be sought from an appropriate REC before Participants are entered into this clinical trial. Participants will only be allowed to enter the study once either they have provided written informed consent. The principle investigator will be responsible for updating the Ethics committee of any new information related to the study.

10.2 Informed consent

Written consent will be obtained from each trial participant; each participant will receive a signed copy of the consent form. Participants unable to provide written informed consent will be excluded from the study.

The Research Nurse or investigator will explain verbally and in writing the exact nature of the study in writing with the provision of Participant information sheet. This will include the known side-effects that may be experienced, and the risks of participating in this clinical trial. Trial participants will be informed that they are free to withdraw their consent from the study or study treatment at any time.

10.3. Assessment and management of risk

The small amounts of venous blood which will be obtained are safe and do not pose any additional risk. All procedures for venepuncture will be fulfilled to ensure safety of participants and the procedure will be carried out by trained medical practitioner, member of InflammaTENSION team.

The study is classified as Type A = No higher than the risk of standard medical care

10.4. Blinding

Patient data will be pseudo-anonymised with a study number given to the patient. This study number will be used for blood tubes. These numbers will be used for blinding. All investigators performing clinical and laboratory assessment will be blinded towards hypertension status and group allocation of individual subjects.

Only the Chief Investigator and research fellow trained who is a member of the direct care team will have access to the participants' personal data during the study. These procedures will comply with the 1998 Data Protection Act. Biological samples collected from participants as part of this study will be transported, stored, accessed and processed in accordance with national legislation relating to the use and storage of human tissue for research purposes and such activities will meet the requirements as set out in the 2004 Human Tissue Act and the 2006 Human Tissue (Scotland) Act.

11. Insurance and Indemnity

The InflammaTENSION study is sponsored by NHS GGC. The sponsor will be liable for negligent harm.. NHS indemnity is provided under the Clinical Negligence and Other Risks Indemnity Scheme (CNORIS). Non-negligent harm from the protocol, design of the study and which is therefore non-negligent, will be covered by the University of Glasgow.

The NHS has a duty of care to Participants treated, whether or not the Participant is taking part in a research study, and the NHS remains liable for clinical negligence and other negligent harm to Participants under its duty of care.

12. Funding

Funding for the InflammaTENSION study will be from the European Research Council and the BHF Centre of Excellence Award.

Grant Funder: European Research Council and British Heart Foundations

Grant award number: ERC Grant agreement in negotiations; BHF - RE/13/5/30177

13. Dissemination of Findings

The research findings will be disseminated to healthcare professionals and public health specialists through newsletters; to members of the public by newspapers and other media as well as by information sessions; and to the wider scientific community through peer reviewed publications and presentations.

No identifiable participant information will be detailed within the research findings

14. References

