Sample Size:	120 hypertensive 120 controls

Screening:	Initial Screening by the clinical care team at a routine outpatient appointment with subsequent verification by a member of InflammaTENSION team (who are also member of the clinical care team for hypertensive patients).
Registration/Randomisation:	No randomization
Main Inclusion Criteria:	
Age between 18-50 years
 
Cases: Office blood pressure ≥ 140 and ≥ 90
 
Controls: Office blood pressure < 140 and < 90 and age, sex and BMI matching to cases

Main Exclusion Criteria:	
(a) Age > 50 years old;
 
(b) Secondary hypertension (including e.g. adrenal tumours, pheochromocytoma, renal artery stenosis; thyroid disease)
 
(c) Acute inflammatory disorders incl. flu, rhinitis, sinusitis etc. within 3 weeks; hospitalization within the past 3 months; Life expectancy of < 3 years; History of alcohol/substance abuse
 
(d) Allergic disorders; chronic infections, COPD, tuberculosis; hepatitis B or C; pneumonitis, bronchiectasis; pericardial or pleural effusion, ascites; liver disease;
 
(e) Chronic inflammatory/autoimmune conditions such (e.g. SLE, rheumatoid arthritis, ulcerative colitis/Crohn's disease; non-basal cell malignancy or myelo- or lymphoproliferative disease within the past 5 years; known HIV+; Immunizations (3 months); pulmonary hypertension;
 
(f) Pregnancy, nursing;
 
(g) History of symptomatic coronary artery disease (events) or heart failure;
 
(h) BMI > 35, diabetes/glucose intolerance (fasting glucose, HbA1; testing, glucose challenge where indicated);
 
(i) Known albuminuria/microalbuminuria; GFR < 60 mL/min/1.73m².
 
(j) Any chronic concurrent treatment. Use of systemic or local steroids/immunosuppressive agents (within 6 months) of the inclusion; Current (within past 3 months) use of anti-hypertensive medication;
 
(k) Major depressive illness or other psychiatric conditions.
 
(l) Participants who decline participation in the study or who are unable to provide informed consent

Product, Dose, Modes of Administration:	N/A
Duration of Treatment:	N/A
Statistical Analysis:	Institute of Cardiovascular and Medical Sciences; University of Glasgow ([name])

InflammaTENSION Study Flowchart

Figure 1: InflammaTENSION Study Flowchart

Study Schedule of InflammaTENSION Study

Table 1: Study Schedule of InflammaTENSION Study

Study Schedule	Procedure Details	

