1.4 Study hypothesis

We hypothesize that primary hypertension is associated with distinct pattern of changes within immune/inflammatory systems consisting of cytokines/chemokines and individual immune cell populations and that this immune signature corresponds with vascular, renal or cognitive phenotypes of hypertension.

2. Study Objectives

The InflammaTENSION pilot study is an observational study aiming to define the cytokine and cellular immune signature of primary hypertension.

- **Primary Endpoint**

Cytokine and cellular immune signature of primary hypertension

- **Secondary Endpoints**

1. Relationships and predictive value of the immune signature of hypertension and clinical phenotypes of hypertension

- Predictive value of immune signature for blood pressure parameters measured by ambulatory blood pressure measurements (ABPM)
- Predictive value of immune signature for endothelial function assessed by Endo-PAT2000 and flow mediated dilatation (FMD) both complementary non-invasive techniques.
- Predictive value of immune signature for vascular stiffness and central pressure assessed by Sphygmocor
- Predictive value of immune signature for renal function parameters
- Predictive value of immune signature for cognitive function

2. To define genetic determinants of immune signature of hypertension which could be used for future mendelian randomization studies.

3. Study Design

The InflammaTENSION study will be performed according to the Research Governance Framework for Health and Community Care (Second edition, 2006).

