3.2 Inclusion criteria

➤ Age between 18-50 years

➤ Cases: Office blood pressure ≥ 140 and ≥ 90 .

Controls: Office blood pressure < 140 and < 90 and age, sex and BMI matching to cases

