3.4.3. Consent at Baseline Visit

All participants will have to provide written consent to take part in the study, the consent taken will be inclusive for the InflammaTENSION study and must be obtained before any of the study procedures can commence. All participants will be provided with a signed copy of their consent form. .

The Chief Investigator (PI) will retain overall responsibility for the informed consent of participants and will ensure that any person delegated responsibility to participate in the informed consent process is duly authorized, trained and competent to participate according to the ethically approved protocol, principles of Good Clinical Practice (GCP) and Declaration of Helsinki.

Informed consent will be obtained prior to the participant undergoing procedures that are specifically for the purposes of the study and are out-with standard routine care.

The right of a participant to refuse participation without giving reasons will be respected.

Before consent is taken the InflammaTENSION investigator will:

- Ensure that the participant has read the PIL and has had ≥ 24 hours to reflect upon the information
- Explain the study to the participant
- Go through detailed inclusion and exclusion criteria for the study**
- Answer any of their questions relating to the study
- Explain that participation in the study is entirely voluntary and they do not have any obligation to take part in the study and they can leave the study at any point***

The process of consent will involve:

- a discussion between the potential participant and an individual knowledgeable about the research about the nature and objectives of the trial and possible risks associated with their participation
- the presentation of written material (e.g., information leaflet and consent document which must be approved by the REC and be in compliance with GCP, local regulatory requirements and legal requirements)
- the opportunity for potential participants to ask questions
- Assessment of capacity: for consent to be ethical and valid in law, participants must be capable of giving consent for themselves. A capable person will:
 - understand the purpose and nature of the research
 - understand what the research involves, its benefits (or lack of benefits), risks and burdens
 - understand the alternatives to taking part
 - be able to retain the information long enough to make an effective decision
 - be able to make a free choice

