Recording of Study Information: The data from the study procedures will be recorded in the electronic case report form (e.g. CASTOR EDC).

Study Procedures Performed at the Baseline Visit will include:

(Please refer to the InflammaTENSION Study Manual of Procedures for more details relating to the study procedures)

- Demographic History
- Medical History
- Height and Weight
- Urine Sample
- Office Blood Pressure measurement – 3 times following 5 minutes of rest
- Venous Blood Sample (40ml) for Blood Tests and Immune signature/Biomarker analysis
- Venous Blood Sample (10ml) for storage for subsequent genetic analysis
- Ambulatory Blood Pressure Monitor Installation if no ABPM performed within past 3 months
- Subjects will be given an IDQ questionnaire (The Interheart Diet Questionnaire) to be returned during visit 1

All procedures will be performed in both Cases and Control groups including ABPM as it will ensure that hypertension is not missed by office blood pressure readings.

Anonymisation

- Patient data will be pseudo-anonymised with a study number given to the patient. This study number will be used for blood tubes. The study specific number will be used for all storage of electronic and paper data relating to the:
 - Vascular function determinations
 - Immune signature determinations (cytokine/chemokine and cellular)
 - Cognitive function questionnaires
 - Will be blinded towards hypertension status and group allocation.
- Only the Chief Investigator, and designated and trained research fellow, who is a member of the direct care team, will have access to the participants' personal data during the study. These procedures will comply with the 1998 Data Protection Act. Biological samples collected from participants as part of this study will be transported, stored, accessed and processed in accordance with national legislation relating to the use and storage of human tissue for research purposes and such activities will meet the requirements as set out in the 2004 Human Tissue Act and the 2006 Human Tissue (Scotland) Act.

Visit 1 (CRF)

Study Procedures performed at Visit 1 at CRF (either in combination with baseline or up to 72h after baseline Visit)

NB: There is no need for a study specific ABPM if a routine care ABPM has been performed within the past 3 months.

This visit will take approximately 2-3.5 the following study procedures will be performed at the final visit.

- Questionnaires
 - ✓ MCQ The Mild Cognitive Impairment Questionnaire

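### Section 10.4 promises blinding of every clinical assessor, which cannot hold for the blood pressure measures or eligibility checks and is not assured for the face-to-face vascular and cognitive outcomes

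*Combined protocol and SAP*

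**What the plan says.** Section 10.4 (Blinding) makes a universal statement: "All investigators performing clinical and laboratory assessment will be blinded towards hypertension status and group allocation of individual subjects". It gives one means of achieving this, the study number used on blood tubes: "These numbers will be used for blinding".

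The Anonymisation list under the Baseline Visit in section 4.4 makes a matching statement. It says the study number will be used to store electronic and paper data on vascular function, the immune signature and the cognitive questionnaires, and it ends: "Will be blinded towards hypertension status and group allocation".

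Other sections describe who learns a participant's status:

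- Section 3.2 defines the groups by office blood pressure: "Cases: Office blood pressure ≥ 140 and ≥ 90", with controls below both limits.
- The Screening row of the Study Synopsis provides for "subsequent verification by a member of InflammaTENSION team (who are also member of the clinical care team for hypertensive patients".
- Section 3.4.3 has the study investigator do the following before consent: "Go through detailed inclusion and exclusion criteria for the study".
- Section 4.4 makes office blood pressure, and ABPM where no recent one exists, Baseline Visit procedures in both groups.
- Section 2 lists as a secondary endpoint: "Predictive value of immune signature for vascular stiffness and central pressure assessed by Sphygmocor".

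**The concern.** A study number hides group from someone who handles only a tube or a file. It does not hide group from someone who reads the blood pressure, checks the entry criteria, or sits with the participant. Section 10.4 makes no such distinction, so every clinical outcome would be reported as blinded.

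The risk concerns secondary outcomes that may depend on an operator or interviewer: FMD, carotid thickness and the cognitive tests. If expectation moves those readings in one group, the shift runs along the case-control contrast. Cytokines that differ between groups would then correlate with the phenotype in a pooled analysis even where no biological link exists.

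**Working it through.** **Step 1. Compare the blinding statement with each procedure.** The protocol gives no figure here, so there is none to reproduce.

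| Activity | What the person sees | Can section 10.4 hold? |
|---|---|---|
| Laboratory assays | Coded tube | Yes |
| Eligibility verification (Synopsis; 3.4.3) | Entry criteria, including the blood pressure rule | No |
| Office blood pressure (4.4) | The variable that defines the entry groups (3.2) | No |
| ABPM (4.4) | For whoever reads it, the measure of hypertensive status (4.5.1) | No |
| SphygmoCor central pressure (2) | A pressure | No |
| FMD, carotid, Endo-PAT, cognitive tests (4.4, Visit 1) | Depends on who performs them, which is not stated | Not assured |

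Two features add to the doubt in the last row. Section 4.4 allows the Baseline Visit and Visit 1 to be combined in one day, so blood pressure and Visit 1 measures can fall in one session. Section 3.4.1 recruits from a blood pressure clinic and seeks matched controls in pre-operative orthopaedics, so a participant may disclose status in conversation.

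**Step 2. Illustrate the size.** The planned secondary analyses are associations of cytokine levels with phenotypes (4.5.2), so the illustration uses a pooled correlation.

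Inputs:
- 120 per group, 240 in all (6.2).
- Cytokine difference *d* between groups. Section 6.2 gives 116 subjects for IL-6 and 58 for TNF-alpha, at two-sided alpha 0.1% and power 90%. Taking both as per group (an assumption), the normal approximation *d* = (3.291 + 1.282) × √(2/n) gives 0.60 and 0.85. With the t distribution these become about 0.61 and 0.87.
- Assessor shift *s* in one group: 0.1, 0.2 or 0.3 SD. This is assumed; the documents give no value.
- No cytokine-phenotype association within either group, and no adjustment for group.

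Formulas: the induced correlation is ρ = (*ds*/4) / √[(1 + *d*²/4)(1 + *s*²/4)]. With z = atanh(ρ) × √(240 − 3), the two-sided 5% false-positive rate is Φ(z − 1.96) + Φ(−z − 1.96).

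| *d* | *s* | ρ | z | False-positive rate |
|---|---|---|---|---|
| 0.61 | 0.1 | 0.015 | 0.22 | 5.6% |
| 0.61 | 0.2 | 0.029 | 0.45 | 7.3% |
| 0.61 | 0.3 | 0.043 | 0.67 | 10.2% |
| 0.87 | 0.1 | 0.020 | 0.31 | 6.1% |
| 0.87 | 0.2 | 0.040 | 0.61 | 9.4% |
| 0.87 | 0.3 | 0.059 | 0.91 | 14.9% |

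Simulation of the same set-up agreed to within 0.2 percentage points. If 116 is instead a total (58 per group), IL-6 moves to the second block.

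**The case against.** The strongest reply is that the documents leave room for separate assessors. They do not name who takes the office readings, who fits the ABPM, or who performs FMD, carotid, Endo-PAT or cognitive testing. Section 3.4.1 mentions a research nurse team, and section 10.4 limits personal-data access to the Chief Investigator and one research fellow. Procedural detail is deferred to a manual that is not among the documents. Section 4.4 already codes the stored vascular and cognitive data and says they will be blinded.

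Most of this stands. A reader might infer that the hypertension care team takes the blood pressures, fits the monitors and then performs the Visit 1 tests, so that the vascular and cognitive outcomes are certainly unblinded. The documents do not support that: the staff are unnamed, and for blood pressure clinic patients the diagnostic ABPM is routine care before the study visit.

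A reader might also size the bias with a two-group t-test on the phenotype, which gives much larger error rates. That is not the analysis listed in sections 2 and 4.5.2. A shift reaches the planned associations only through the cytokine's own group difference, and adjusting for group would remove a constant shift.

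Carotid thickness is a study procedure but is not named as an outcome in section 2 or 4.5, and the documents do not say how each cognitive test is administered.

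The reply does not rescue the universal claim. Whatever the manual says, whoever measures office blood pressure or SphygmoCor central pressure sees a blood pressure, and whoever verifies eligibility learns the group. Coding stored data also does not mask the person who acquired them.

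**Conclusion.** The statement in section 10.4, and its counterpart in section 4.4, is wrong as written. It is false for office blood pressure, ABPM, central pressure and eligibility verification. For FMD, carotid, Endo-PAT and interviewer-administered cognitive outcomes, blinding is claimed without a named assessor or other safeguard beyond coding, and so is not assured. The laboratory assays behind the primary outcome are untouched.

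The consequence for the secondary associations is moderate at most on the values tried: from 5% to about 6-10% false positives at a cytokine difference of about 0.61 SD, and to about 6-15% at about 0.87 SD. These figures rest on assumed shifts of 0.1 to 0.3 SD, on reading section 6.2 as subjects per group, on planning differences rather than observed ones, and on a pooled analysis without adjustment for group. The contradiction in the text does not depend on them. The correction should be made because it is cheap and keeps an unsupported claim out of the report.

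**What to change.** 1. Limit the blinding claim in sections 10.4 and 4.4 to laboratory assays and offline reading of recordings.
2. Save the FMD, carotid and Endo-PAT recordings and the SphygmoCor stiffness traces under study number, with blood pressure and group fields hidden. Have the existing readers analyse them in batches and in random order.
3. State who performs or reads each Visit 1 measure, and that readers have no access to eligibility or blood pressure data. If the manual already says so, refer to it.
4. Report office blood pressure, ABPM, central pressure and any cognitive test given by someone aware of status as assessor-aware.

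The cost is protocol wording and a coded file export. Coded storage is already planned, and no extra staff, participants or visits are needed. The small downside is that readings are made in batches rather than on the day. Masked reading protects the reading step only; it does not mask the person who acquires the recording.
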